5.2 SAFETY PARAMETERS AND DEFINITIONS

Safety assessments will consist of monitoring and recording adverse events, including SAEs and adverse events of special interest, performing protocol-specified safety laboratory assessments, measuring protocol-specified vital signs, and conducting other protocol-specified tests that are deemed critical to the safety evaluation of the study.

Certain types of events require immediate reporting to the Sponsor, as outlined in Section [5.4](#).

5.2.1 Adverse Events

According to the ICH guideline for Good Clinical Practice, an adverse event is any untoward medical occurrence in a clinical investigation subject administered a pharmaceutical product, regardless of causal attribution. An adverse event can therefore be any of the following:

- Any unfavourable and unintended sign (including an abnormal laboratory finding), symptom, or disease temporally associated with the use of a medicinal product, whether or not considered related to the medicinal product
- Any new disease or exacerbation of an existing disease (a worsening in the character, frequency, or severity of a known condition) (see Sections [5.3.5.9](#) and [5.3.5.10](#) for more information)
- Recurrence of an intermittent medical condition (e.g., headache) not present at baseline
- Any deterioration in a laboratory value or other clinical test (e.g., ECG, X-ray) that is associated with symptoms or leads to a change in study treatment or concomitant treatment or discontinuation from study treatment
- Adverse events that are related to a protocol-mandated intervention, including those that occur prior to assignment of study treatment (e.g., screening invasive procedures such as biopsies)

5.2.2 Serious Adverse Events (Immediately Reportable to the Sponsor)

A serious adverse event is any adverse event that meets any of the following criteria:

- Is fatal (i.e., the adverse event actually causes or leads to death)

- Is life threatening (i.e. the adverse event, in the view of the investigator, places the patient at immediate risk of death)
- This does not include any adverse event that, had it occurred in a more severe form or was allowed to continue, might have caused death.
- Requires or prolongs inpatient hospitalization (see Section [5.3.5.11](#))
- Results in persistent or significant disability/incapacity (i.e. the adverse event results in substantial disruption of the patient's ability to conduct normal life functions)
- Is a congenital anomaly/birth defect in a neonate/infant born to a mother exposed to study treatment
- Is a significant medical event in the investigator's judgment (e.g., may jeopardize the patient or may require medical/surgical intervention to prevent one of the outcomes listed above)

The terms "severe" and "serious" are not synonymous. Severity refers to the intensity of an adverse event (e.g., rated as mild, moderate, or severe, or according to NCI CTCAE; see Section [5.3.3](#)); the event itself may be of relatively minor medical significance (such as severe headache without any further findings).

Severity and seriousness need to be independently assessed for each adverse event recorded on the eCRF.

SAEs are required to be reported by the investigator to the Sponsor immediately (i.e. no more than 24 hours after learning of the event; see Section [5.4.2](#) for reporting instructions).

5.2.3 Adverse Events of Special Interest (Immediately Reportable to the Sponsor)

Adverse events of special interest are required to be reported by the investigator to the Sponsor immediately (i.e. no more than 24 hours after learning of the event; see Section [5.4.2](#) for reporting instructions).

These events may or may not be SAEs and they may or may not be considered related to study medication. Regardless of relationship or severity, these events will be recorded if they start from the time of the first dose of study treatment and will be followed until resolution.

After the end of the adverse event reporting period, the Sponsor should be notified if the Investigator becomes aware of any adverse events of special interest that are believed to be related to prior study treatment.

Adverse events of special interest for this study are as follows:

Events specific to cobimetinib and vemurafenib

- Any RVO
- Serous retinopathy, including events of retinal detachment, retinal pigment epithelium detachment, neurosensory retinal detachment or central serous chorioretinopathy
- Grade ≥ 3 photosensitivity
- Rhabdomyolysis or Grade ≥ 3 CPK elevation
- Grade ≥ 3 haemorrhage or any grade cerebral haemorrhage
- Grade ≥ 3 rash
- Grade ≥ 3 diarrhoea
- Grade ≥ 3 QT interval prolongation
- Symptomatic heart failure and/or Grade ≥ 2 left ventricular ejection fraction reduction
- Pneumonitis
- Hepatitis, including AST or ALT $> 10 \times$ ULN

Events specific to atezolizumab

- Pneumonitis
- Colitis
- Endocrinopathies: diabetes mellitus, pancreatitis, adrenal insufficiency, hyperthyroidism, or hypophysitis
- Hepatitis, including AST or ALT $> 10 \times$ ULN
- Systemic lupus erythematosus
- Neurological disorders: Guillain-Barré syndrome, myasthenia gravis, meningoencephalitis
- Nephritis
- Events suggestive of hypersensitivity, IRRs, CRS, influenza-like illness, *HLH, and MAS*
- Ocular toxicities (e.g., uveitis, retinitis, optic neuritis)
- Myositis
- Myopathies, including rhabdomyolysis
- Grade ≥ 2 cardiac disorders (e.g., atrial fibrillation, myocarditis, pericarditis)
- Vasculitis
- Autoimmune haemolytic anaemia

- Severe cutaneous reactions (e.g., Stevens-Johnson syndrome, dermatitis bullous, toxic epidermal necrolysis)

Other adverse events of special interest

- Cases of potential drug-induced liver injury that include an elevated ALT or AST in combination with either an elevated bilirubin or clinical jaundice, as defined by Hy's Law (see Section 5.3.5.7)
- Suspected transmission of an infectious agent by the study treatment, as defined below

Any organism, virus, or infectious particle (e.g., prion protein transmitting transmissible spongiform encephalopathy), pathogenic or non-pathogenic, is considered an infectious agent. A transmission of an infectious agent may be suspected from clinical symptoms or laboratory findings that indicate an infection in a patient exposed to a medicinal product. This term applies only when a contamination of study treatment is suspected.

5.3 METHODS AND TIMING FOR CAPTURING AND ASSESSING SAFETY PARAMETERS

The investigator is responsible for ensuring that all adverse events (see Section 5.2.1 for definition) are recorded on the Adverse Event eCRF and reported to the Sponsor in accordance with instructions provided in this section and in Sections 5.4–5.6.

For each adverse event recorded on the Adverse Event eCRF, the investigator will make an assessment of seriousness (see Section 5.2.2 for seriousness criteria), severity (see Section 5.3.3) and causality (see Section 5.3.4).

5.3.1 Adverse Event Reporting Period

Investigators will seek information on adverse events at each patient contact. All adverse events, whether reported by the patient or noted by study personnel, will be recorded in the patient's medical record and on the Adverse Event eCRF.

After informed consent has been obtained but prior to initiation of study treatment, only SAEs caused by a protocol-mandated intervention (e.g., invasive procedures such as biopsies, discontinuation of medications) should be reported (see Section 5.4.2 for instructions for reporting SAEs).

After initiation of study treatment, all adverse events as follows:

- All adverse events will be reported until 30 days after the last dose of study treatment or until initiation of new systemic anti-cancer therapy, whichever occurs first
- SAEs and adverse events of special interest will continue to be reported until 90 days after the last dose of study treatment or until initiation of new systemic anti-cancer therapy, whichever occurs first.

- Subsequently, the Sponsor should be notified if the investigator becomes aware of any SAE that is believed to be related to prior study treatment.

Instructions for reporting adverse events that occur after the adverse event reporting period are provided in Section 5.6.

5.3.2 Eliciting Adverse Event Information

A consistent methodology of non-directive questioning should be adopted for eliciting adverse event information at all patient evaluation timepoints. Examples of non-directive questions include the following:

"How have you felt since your last clinic visit?"

"Have you had any new or changed health problems since you were last here?"

5.3.3 Assessment of Severity of Adverse Events

The adverse event severity grading scale for the NCI CTCAE (v4.0) will be used for assessing adverse event severity. Table 6 will be used for assessing severity for adverse events that are not specifically listed in the NCI CTCAE.

Table 6 Adverse Event Severity Grading Scale for Events Not Specifically Listed in NCI CTCAE

Grade	Severity
1	Mild; asymptomatic or mild symptoms; clinical or diagnostic observations only; or intervention not indicated
2	Moderate; minimal, local, or non-invasive intervention indicated; or limiting age-appropriate instrumental activities of daily living [a]
3	Severe or medically significant, but not immediately life-threatening; hospitalization or prolongation of hospitalization indicated; disabling; or limiting self-care activities of daily living [b, c]
4	Life-threatening consequences or urgent intervention indicated [d]
5	Death related to adverse event [d]

NCI CTCAE = National Cancer Institute Common Terminology Criteria for Adverse Events.

Note: Based on the most recent version of NCI CTCAE (v4.0), which can be found at:

http://ctep.cancer.gov/protocolDevelopment/electronic_applications/ctc.htm

- Instrumental activities of daily living refer to preparing meals, shopping for groceries or clothes, using the telephone, managing money, etc.
- Examples of self-care activities of daily living include bathing, dressing and undressing, feeding oneself, using the toilet, and taking medications, as performed by patients who are not bedridden.
- If an event is assessed as a "significant medical event," it must be reported as an SAE (see Section 5.4.2 for reporting instructions), per the definition of SAEs in Section 5.2.2.
- Grade 4 and 5 events must be reported as SAEs (see Section 5.4.2 for reporting instructions), per the definition of SAEs in Section 5.2.2.

5.3.4 Assessment of Causality of Adverse Events

Investigators should use their knowledge of the patient, the circumstances surrounding the event, and an evaluation of any potential alternative causes to determine whether an adverse event is considered to be related to study treatment, indicating "yes" or "no" accordingly. The following guidance should be taken into consideration (see also [Table 7](#)):

- Temporal relationship of event onset to the initiation of study treatment
- Course of the event, with special consideration of the effects of dose reduction, discontinuation of study treatment, or reintroduction of study treatment (as applicable)
- Known association of the event with study treatment or with similar treatments
- Known association of the event with the disease under study
- Presence of risk factors in the patient or use of concomitant medications known to increase the occurrence of the event
- Presence of non-treatment-related factors that are known to be associated with the occurrence of the event

Table 7 Causal Attribution Guidance

Is the adverse event suspected to be caused by study treatment on the basis of facts, evidence, science-based rationales, and clinical judgment?	
YES	There is a plausible temporal relationship between the onset of the adverse event and administration of study treatment, and the adverse event cannot be readily explained by the patient's clinical state, intercurrent illness, or concomitant therapies; and/or the adverse event follows a known pattern of response to study treatment; and/or the adverse event abates or resolves upon discontinuation of study treatment or dose reduction and, if applicable, reappears upon re-challenge.
NO	An adverse event will be considered related, unless it fulfils the criteria specified below. Evidence exists that the adverse event has an aetiology other than study treatment (e.g., pre-existing medical condition, underlying disease, intercurrent illness, or concomitant medication); and/or the adverse event has no plausible temporal relationship to administration of study treatment (e.g., cancer diagnosed two days after first dose of study treatment).

For patients receiving combination therapy, causality will be assessed individually for each protocol-mandated therapy.

5.3.5 Procedures for Recording Adverse Events

Investigators should use correct medical terminology/concepts when recording adverse events on the Adverse Event eCRF. Avoid colloquialisms and abbreviations.

Only one adverse event term should be recorded in the event field on the Adverse Event eCRF.

Cobimetinib, atezolizumab, vemurafenib — F. Hoffmann-La Roche Ltd

106 / Protocol MO39136, Version 5.0

5.3.5.1 Infusion-Related Reactions

Adverse events that occur during or within 24 hours after study treatment administration and are judged to be related to study treatment infusion should be captured as a diagnosis (e.g., "infusion-related reaction") on the Adverse Event eCRF. If possible, avoid ambiguous terms such as "systemic reaction." Associated signs and symptoms should be recorded on the dedicated Infusion-Related Reaction eCRF. If a patient experiences both a local and systemic reaction to the same dose of study treatment, each reaction should be recorded separately on the Adverse Event eCRF, with signs and symptoms also recorded separately on the dedicated Infusion-Related Reaction eCRF.

5.3.5.2 Diagnosis versus Signs and Symptoms

A diagnosis (if known) should be recorded on the Adverse Event eCRF rather than individual signs and symptoms (e.g., record only liver failure or hepatitis rather than jaundice, asterixis and elevated transaminases). However, if a constellation of signs and/or symptoms cannot be medically characterized as a single diagnosis or syndrome at the time of reporting, each individual event should be recorded on the Adverse Event eCRF. If a diagnosis is subsequently established, all previously reported adverse events based on signs and symptoms should be nullified and replaced by one adverse event report based on the single diagnosis, with a starting date that corresponds to the starting date of the first symptom of the eventual diagnosis.

5.3.5.3 Adverse Events That Are Secondary to Other Events

In general, adverse events that are secondary to other events (e.g., cascade events or clinical sequelae) should be identified by their primary cause, with the exception of severe or serious secondary events. A medically significant secondary adverse event that is separated in time from the initiating event should be recorded as an independent event on the Adverse Event eCRF. For example:

- If vomiting results in mild dehydration with no additional treatment in a healthy adult, only vomiting should be reported on the eCRF.
- If vomiting results in severe dehydration, both events should be reported separately on the eCRF.
- If a severe gastrointestinal haemorrhage leads to renal failure, both events should be reported separately on the eCRF.
- If dizziness leads to a fall and consequent fracture, all three events should be reported separately on the eCRF.
- If neutropenia is accompanied by an infection, both events should be reported separately on the eCRF.

All adverse events should be recorded separately on the Adverse Event eCRF if it is unclear as to whether the events are associated.

5.3.5.4 Persistent or Recurrent Adverse Events

A persistent adverse event is one that extends continuously, without resolution, between patient evaluation timepoints. Such events should only be recorded once on the Adverse Event eCRF. The initial severity (intensity or grade) of the event will be recorded at the time the event is first reported. If a persistent adverse event becomes more severe, the most extreme severity should also be recorded on the Adverse Event eCRF. If the event becomes serious, it should be reported to the Sponsor immediately (i.e., no more than 24 hours after learning that the event became serious; see Section [5.4.2](#) for reporting instructions). The Adverse Event eCRF should be updated by changing the event from "non-serious" to "serious," providing the date that the event became serious, and completing all data fields related to SAEs.

A recurrent adverse event is one that resolves between patient evaluation timepoints and subsequently recurs. Each recurrence of an adverse event should be recorded as a separate event on the Adverse Event eCRF.

5.3.5.5 Abnormal Laboratory Values

Not every laboratory abnormality qualifies as an adverse event. A laboratory test result must be reported as an adverse event if it meets any of the following criteria:

- Is accompanied by clinical symptoms
- Results in a change in study treatment (e.g., dosage modification, treatment interruption, or treatment discontinuation)
- Results in a medical intervention (e.g., potassium supplementation for hypokalaemia) or a change in concomitant therapy
- Is clinically significant in the investigator's judgment

It is the investigator's responsibility to review all laboratory findings. Medical and scientific judgment should be exercised in deciding whether an isolated laboratory abnormality should be classified as an adverse event.

If a clinically significant laboratory abnormality is a sign of a disease or syndrome (e.g., ALP and bilirubin 5 × ULN associated with cholestasis), only the diagnosis (i.e., cholestasis) should be recorded on the Adverse Event eCRF.

If a clinically significant laboratory abnormality is not a sign of a disease or syndrome, the abnormality itself should be recorded on the Adverse Event eCRF, along with a descriptor indicating whether the test result is above or below the normal range (e.g., "elevated potassium," as opposed to "abnormal potassium"). If the laboratory abnormality can be characterized by a precise clinical term per standard definitions, the clinical term should be recorded as the adverse event. For example, an elevated serum potassium level of 7.0 mEq/L should be recorded as "hyperkalaemia."

Observations of the same clinically significant laboratory abnormality from visit to visit should only be recorded once on the Adverse Event eCRF (see Section [5.3.5.4](#) for details on recording persistent adverse events).

5.3.5.6 Abnormal Vital Sign Values

Not every vital sign abnormality qualifies as an adverse event. A vital sign result must be reported as an adverse event if it meets any of the following criteria:

- Is accompanied by clinical symptoms
- Results in a change in study treatment (e.g., dosage modification, treatment interruption, or treatment discontinuation)
- Results in a medical intervention or a change in concomitant therapy
- Is clinically significant in the investigator's judgment

It is the investigator's responsibility to review all vital sign findings. Medical and scientific judgment should be exercised in deciding whether an isolated vital sign abnormality should be classified as an adverse event.

If a clinically significant vital sign abnormality is a sign of a disease or syndrome (e.g., high blood pressure), only the diagnosis (i.e., hypertension) should be recorded on the Adverse Event eCRF.

Observations of the same clinically significant vital sign abnormality from visit to visit should only be recorded once on the Adverse Event eCRF (see Section [5.3.5.4](#) for details on recording persistent adverse events).

5.3.5.7 Abnormal Liver Function Tests

The finding of an elevated ALT or AST ($> 3 \times$ baseline value) in combination with either an elevated total bilirubin ($> 2 \times$ ULN) or clinical jaundice in the absence of cholestasis or other causes of hyperbilirubinemia is considered to be an indicator of severe liver injury (as defined by Hy's Law). Therefore, investigators must report as an adverse event the occurrence of either of the following:

- Treatment-emergent ALT or AST $> 3 \times$ baseline value in combination with total bilirubin $> 2 \times$ ULN (of which $\geq 35\%$ is direct bilirubin)
- Treatment-emergent ALT or AST $> 3 \times$ baseline value in combination with clinical jaundice

The most appropriate diagnosis or (if a diagnosis cannot be established) the abnormal laboratory values should be recorded on the Adverse Event eCRF (see Section [5.3.5.2](#)) and reported to the Sponsor immediately (i.e., no more than 24 hours after learning of the event), either as an SAE or an adverse event of special interest (see Section [5.4.2](#)).

5.3.5.8 Deaths

For this protocol, mortality is an efficacy endpoint. Deaths that occur during the protocol-specified adverse event reporting period (see Section 5.3.1) that are attributed by the investigator solely to progression of metastatic melanoma should be recorded on the Death Attributed to Progressive Disease eCRF. All other on-study deaths, regardless of relationship to study treatment, must be recorded on the Adverse Event eCRF and immediately reported to the Sponsor (see Section 5.4.2).

Death should be considered an outcome and not a distinct event. The event or condition that caused or contributed to the fatal outcome should be recorded as the single medical concept on the Adverse Event eCRF. Generally, only one such event should be reported. The term "**sudden death**" should be used only for the occurrence of an abrupt and unexpected death due to presumed cardiac causes in a patient with or without pre-existing heart disease, within one hour after the onset of acute symptoms or, in the case of an unwitnessed death, within 24 hours after the patient was last seen alive and stable. If the cause of death is unknown and cannot be ascertained at the time of reporting, "**unexplained death**" should be recorded on the Adverse Event eCRF. If the cause of death later becomes available (e.g., after autopsy), "unexplained death" should be replaced by the established cause of death.

Deaths that occur after the adverse event reporting period should be reported as described in Section 5.6.

5.3.5.9 Pre-existing Medical Conditions

A pre-existing medical condition is one that is present at the screening visit for this study. Such conditions should be recorded on the General Medical History and Baseline Conditions eCRF.

A pre-existing medical condition should be recorded as an adverse event only if the frequency, severity, or character of the condition worsens during the study. When recording such events on the Adverse Event eCRF, it is important to convey the concept that the pre-existing condition has changed by including applicable descriptors (e.g., "more frequent headaches").

5.3.5.10 Lack of Efficacy or Worsening of Melanoma

Events that are clearly consistent with the expected pattern of progression of the underlying disease should not be recorded as adverse events. These data will be captured as efficacy assessment data only. In most cases, the expected pattern of progression will be based on RECIST v1.1. In rare cases, the determination of clinical progression will be based on symptomatic deterioration. However, every effort should be made to document progression through use of objective criteria. If there is any uncertainty as to whether an event is due to disease progression, it should be reported as an adverse event.

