5.1.1.6 Haemorrhage

Haemorrhage, including major haemorrhages defined as symptomatic bleeding in a critical area or organ, can occur with cobimetinib. In clinical studies with cobimetinib, events of cerebral haemorrhage, gastrointestinal tract haemorrhage, reproductive tract haemorrhage and haematuria, have been reported.

Caution should be used in patients with additional risk factors for bleeding, such as brain metastases, and/or in patients that use concomitant medications that increase the risk of bleeding (including antiplatelet or anticoagulant therapy). Coumarin anticoagulants are not permitted during the study.

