5.3.5.11 Hospitalization or Prolonged Hospitalization

Any adverse event that results in hospitalization (i.e., inpatient admission to a hospital) or prolonged hospitalization should be documented and reported as an SAE (per the definition of SAEs in Section 5.2.2), except as outlined below.

An event that leads to hospitalization under the following circumstances should not be reported as an adverse event or an SAE:

- Hospitalization for respite care
- Planned hospitalization required by the protocol (e.g., for study treatment administration or performance of an efficacy measurement for the study)
- Hospitalization for a pre-existing condition, provided that all of the following criteria are met:
 - The hospitalization was planned prior to the study or was scheduled during the study when elective surgery became necessary because of the expected normal progression of the disease
 - The patient has not experienced an adverse event
- Hospitalization due solely to progression of the underlying cancer

An event that leads to hospitalization under the following circumstances is not considered to be an SAE, but should be reported as an adverse event instead:

- Hospitalization that was necessary because of patient requirement for outpatient care outside of normal outpatient clinic operating hours.

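### The progression exclusion in Protocol 5.3.5.10 and 5.3.5.11 does not exempt AESIs, so a cerebral haemorrhage confidently attributed to a progressing brain metastasis may go unrecorded despite 5.2.3 and 5.4

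*Protocol*

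**What the plan says.** Two sets of recording rules bear on an intracranial bleed.

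The AESI rules are inclusive. Protocol 5.2.3 lists "Grade ≥ 3 haemorrhage or any grade cerebral haemorrhage" among the events specific to cobimetinib and vemurafenib, and says of all AESIs: "Regardless of relationship or severity, these events will be recorded if they start from the time of the first dose of study treatment". The sentence before that one makes clear that relationship means relationship to study medication. Protocol 5.4 then requires AESIs to be reported to the sponsor within 24 hours, again irrespective of relationship to study treatment.

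The progression rules are exclusive. Protocol 5.3.5.10 opens with "Events that are clearly consistent with the expected pattern of progression of the underlying disease should not be recorded as adverse events" and continues: "These data will be captured as efficacy assessment data only". It qualifies this with "In most cases, the expected pattern of progression will be based on RECIST v1.1", allows symptomatic deterioration as the basis only rarely, and ends: "If there is any uncertainty as to whether an event is due to disease progression, it should be reported as an adverse event". Protocol 5.3.5.11 adds "Hospitalization due solely to progression of the underlying cancer" to the admissions that are reported neither as an AE nor as an SAE.

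Neither progression rule mentions AESIs, and neither AESI rule mentions progression.

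**The concern.** Measurable brain metastases are an entry criterion, so a bleed into a growing lesion is foreseeable in any patient in this trial. The protocol itself treats bleeding as important here. Section 5.1.1 names severe haemorrhage as an identified risk of cobimetinib, and 5.1.1.6 says: "Caution should be used in patients with additional risk factors for bleeding, such as brain metastases". Making cerebral haemorrhage of any grade an AESI is a sensible response, because it is meant to capture the event without first asking what caused it.

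The progression rules bring that causal question back at the point of recording. If the investigator answers it confidently in favour of progression, 5.3.5.10 tells the site not to enter the event. At stake are the completeness of one of the more important safety counts in the study, and the 24-hour report that depends on the same entry. There is no control arm against which under-recording could be judged.

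**Working it through.** No formula or planned figure is involved, so the check consists of setting the sections side by side and following one event through them.

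**Inputs**
- Protocol 5.2.1: the AE definition covers exacerbation of an existing disease and refers the reader to 5.3.5.10.
- Protocol 5.3.5.10: events clearly consistent with expected progression are not AEs; doubtful cases are.
- Protocol 5.3.5.11: admission due solely to progression is neither AE nor SAE.
- Protocol 5.3.5.8: a death within the reporting period attributed solely to melanoma progression goes on a separate eCRF.
- Protocol 5.2.3 and 5.4: cerebral haemorrhage of any grade is an AESI, recorded and reported within 24 hours regardless of relationship to study medication.
- Protocol Appendix 5: RECIST v1.1 progression rests on target-lesion diameters, unequivocal non-target progression and new lesions. Bleeding is not a criterion.
- SAP 5.6.2: AESIs are summarised from the coded AE data. SAP 5.6.1: dose modifications and their reasons are summarised by drug.

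**Following one event**
1. A Cohort 2 patient develops a symptomatic bleed in a lesion that has also grown on MRI.
2. Under 5.2.3 and 5.4 the site records it and reports it within 24 hours.
3. Under 5.2.1 and 5.3.5.10, an investigator who is sure that the bleed is part of progression does not record it as an AE. On that reading it never becomes an AESI either, since an AESI is a kind of AE.
4. If the patient is admitted and the investigator considers the admission due solely to progression, 5.3.5.11 removes the hospitalisation route to an SAE report.
5. The closing sentence of 5.3.5.10 restores the event only if the investigator is in doubt. A confident attribution bypasses it.
6. An event missing from the AE data is missing from the AESI tables in SAP 5.6.2.

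Steps 2 and 3 give opposite instructions for the same event, and no sentence in the protocol or SAP ranks them.

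**Size**

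The documents give no expected rate of intracranial bleeding and no basis for estimating how often such an event would be attributed to progression. The arithmetic can therefore give only the effect per omitted patient. With about 60 patients planned for Cohort 2, omitting k affected patients lowers the observed incidence by k/60:
- k = 1: 1/60 = 1.7 percentage points
- k = 2: 2/60 = 3.3 percentage points
- k = 3: 3/60 = 5.0 percentage points

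The values of k are illustrative, and zero is possible.

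**The case against.** The best defence is that the protocol already resolves the matter. The AESI rule is specific and mandatory, and it names the event. The progression rule is general, is worded as guidance, and does not mention haemorrhage. It is confined to clear cases, rests mainly on RECIST v1.1, which has no bleeding criterion, and sends doubtful cases to the AE form. An acute bleed in a patient taking a drug with a known haemorrhage risk is seldom beyond doubt. Table 7 in 5.3.4 also lists underlying disease as a reason to judge an AE unrelated, which implies that disease-caused events are expected on the AE form.

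Much of this stands, and it rules out several stronger readings that a reader might be tempted to draw:
- *That such bleeds are necessarily excluded.* They are not. Exclusion depends on a confident judgement by the investigator.
- *That 5.2.3 requires recording regardless of cause.* It says regardless of relationship, meaning relationship to study medication, and does not address progression.
- *That the event would be lost altogether.* Appendices 12 and 13 call for cobimetinib interruption after cerebral haemorrhage of any grade, and SAP 5.6.1 summarises reasons for dose modification, so some trace should remain. The eCRF and IRC charter, which might capture more, are not among the documents.
- *That the haemorrhage rate is biased by a known amount, or differently by site.* Nothing in the documents supports a figure or a site pattern.

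What the defence does not supply is a sentence saying that 5.2.3 prevails. The AE definition itself points to 5.3.5.10, so a site that follows that reference and is sure of progression has written support for leaving the event off.

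**Conclusion.** The conflict is real but conditional. Protocol 5.3.5.10 and 5.3.5.11 do not exempt AESIs, while 5.2.3 and 5.4 contain no exception for progression. A cerebral haemorrhage confidently judged to be clearly due to a progressing brain metastasis may be left off the Adverse Event eCRF, and so out of the 24-hour report and the AESI tables. The doubt provision limits how often this can happen but does not prevent it.

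The total effect is unknown. The figure of 1.7 percentage points per omitted patient assumes a denominator of 60 treated Cohort 2 patients. SAP 5.6 also groups that cohort by whether atezolizumab was received, and within either group the denominator would be smaller and the effect per patient larger.

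This is more than a missing detail, because it concerns a named AESI in a trial where every patient carries the risk factor that the protocol identifies. It should be corrected, although it does not call the design or the efficacy analysis into question.

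**What to change.** Reconcile the sections by adding one sentence to both 5.3.5.10 and 5.3.5.11, for example: *Adverse events of special interest listed in Section 5.2.3, including cerebral haemorrhage of any grade, are recorded on the Adverse Event eCRF and reported within 24 hours even when the investigator attributes them to disease progression; that attribution is noted with the event.* Section 5.3.5.12 already has a comparable clause, which makes AESIs arising from overdose or medication error immediately reportable.

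The change concerns recording and reporting only and leaves dosing and clinical management untouched. It costs one sentence in two places and matching eCRF guidance. The downside is that the reported AESI rate may be slightly higher and will include some bleeds caused by the disease; the noted attribution lets a reader see which those are. A table in SAP 5.6.2 splitting cerebral haemorrhage by that attribution would be useful but is optional in a descriptive study of this size.
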